  # var. <- w8.list[1]

  if (!var. %in% meal.list) {

    fm. <- paste(var., "~ (", paste(c(

      sub('w8', 'w0', var.)

      , c('sex', 'adherence', "fasting.glucose.w0", "glucose.auc.w0", "insulin.auc.w0")

      , w8.list[!w8.list %in% c(var., meal.list)]

      , c("glucose.auc.w8", "insulin.auc.w8")

    ), collapse=' + '), ')')

    fm.list <- c(fm.list, as.formula(fm.)); rm(fm.)
  }
}

```

```

} else {

  fm. <- paste(var., "~ (" , paste(c(

    sub('w8', 'w0', var.)

    , c('sex', 'adherence', 'fasting.glucose.w0')

    , w8.list[!w8.list %in% c(var.)]

    ), collapse=' + '), '))

  fm.list <- c(fm.list, as.formula(fm.)); rm(fm.)

}

}; rm(var.)

fm.list <- as.list(fm.list)

names(fm.list) <- c(w0.list, w8.list)

```

```
## Drop out & adherence
```

```
fm.list$drop.out <- as.formula('drop.out ~ 1')
```

```
fm.list$adher.w2 <- as.formula('adher.w2 ~ 0 + I(as.numeric(drop.out != "Diet")*as.numeric(week.drop >= 2))')
```

```
fm.list$adher.w4 <- as.formula('adher.w4 ~ 0 + I(as.numeric(drop.out != "Diet")*as.numeric(week.drop >= 4)*as.numeric(adher.w2))')
```

```
fm.list$adher.w8 <- as.formula('adher.w8 ~ 0 + I(as.numeric(drop.out != "Diet")*as.numeric(adher.w2)) + I(as.numeric(drop.out !=  
"Diet")*as.numeric(adher.w4))')
```

```
}
```

```
library(mice)
```

```
# Set up imputation methods
```

```
var.list <- c(w0.list, adher.list, w8.list, calculated.list)
```

```
{
```

```
  mice.fit <- mice(
```

```
    data=temp.data
```

```
    , m=1, maxit=0
```

```
    , blocks=var.list
```

```
    , visitSequent=var.list
```

```
    , formulas=fm.list
```

```
)
```

```
mice.fit$loggedEvents
```

```
method. <- mice.fit$method
```

```
## Construct calculated methods
```

```
{
```

```
method.[names(method.) == 'glucose.auc.w0'] <- gsub(
```

```
'\n', '',
```

```
"~ |("
```

```
log((
```

```
exp(glucose.auc.break.w0)
```

```
+ exp(glucose.auc.lunch.w0)
```

```
+ exp(glucose.auc.dinner.w0)
```

)/3)

)"

)

```
method.[names(method.) == 'insulin.auc.w0'] <- gsub(
```

```
"\n", "
```

```
"~ |("
```

```
log((
```

```
exp(insulin.auc.break.w0)
```

```
+ exp(insulin.auc.lunch.w0)
```

```
+ exp(insulin.auc.dinner.w0)
```

)/3)

```
)"
```

```
)
```

```
method.[names(method.) == 'glucose.auc.w8'] <- gsub(
```

```
"\n", "
```

```
"~ | (
```

```
log((
```

```
exp(glucose.auc.break.w8)
```

```
+ exp(glucose.auc.lunch.w8)
```

```
+ exp(glucose.auc.dinner.w8)
```

```
)/3)
```

```
)"
```

```

)

method.[names(method.) == 'insulin.auc.w8'] <- gsub(

'\n', ", ",

"~ |("

log((

exp(insulin.auc.break.w8)

+ exp(insulin.auc.lunch.w8)

+ exp(insulin.auc.dinner.w8)

)/3)

)"

)

```

```

method.[names(method.) == 'adherence'] <- gsub(

  '\n', "",

  "~ |("

  ((

    as.numeric(adher.w2)

    + as.numeric(adher.w4)

    + 2*as.numeric(adher.w8)

  )/4)

  )"

)

}

```

```
}
```

```
for (treat. in c('A', 'B', 'C')) {
```

```
  mice.fit2 <- mice(
```

```
    data=temp.data[temp.data$treat == treat.,]
```

```
    , m=M., maxit=N.iter
```

```
    , blocks=var.list
```

```
    , visitSequent=var.list
```

```
    , formulas=fm.list
```

```
    , method=method.
```

```
    , print=F
```

```
)
```

```
mice.fit2$loggedEvents
```

```
if (treat. == 'A') mice.fit.A <- mice.fit2
```

```
if (treat. == "B") mice.fit.B <- mice.fit2
```

```
if (treat. == "C") mice.fit.C <- mice.fit2
```

```
rm(mice.fit2)
```

```
}; rm(treat.)
```

```
rm(mice.fit, method., fm.list, var.list)
```

```

if (MNAR.type == 0) mice.full.fit0 <- rbind(rbind(mice.fit.A, mice.fit.B), mice.fit.C)

if (MNAR.type == 1) mice.full.fit1 <- rbind(rbind(mice.fit.A, mice.fit.B), mice.fit.C)

rm(mice.fit.A, mice.fit.B, mice.fit.C)

}; rm(MNAR.type)

rm(M., N.iter, temp.data, adher.list, aux.list, meal.list, calculated.list, w0.list, w8.list)

ls()

#####

## Analyses

#####

```

```
output <- NULL
```

```
for (MNAR.type in 0:1) {
```

```
  if (MNAR.type == 0) mice.full.fit <- mice.full.fit0
```

```
  if (MNAR.type == 1) mice.full.fit <- mice.full.fit1
```

```
library(mice)
```

```
var.list <- c(
```

```
  'glucose.auc', "glucose.auc.break", "glucose.auc.lunch", "glucose.auc.dinner", 'fasting.glucose'
```

```
  , 'insulin.auc', "insulin.auc.break", "insulin.auc.lunch", "insulin.auc.dinner", 'fasting.insulin'
```

```
  , 'weight', "hba1c"
```

```

)

for (var. in var.list) {

  for (visit. in c('.w8')) {

    output <- rbind(output, c(

      c('MI', 'MI-worst')[0:1 == MNAR.type]

      , 'diff - orig'

      , var.

      , toupper(substring(visit.,2,3))

      , summary(pool(with(

        data = mice.full.fit

        , expr = eval(parse(text=paste('lm(l(', var., visit., ' - ', var., '.w0) ~ 0 + treat + sex + l(', var., '.w0 - mean(', var., '.w0))))', sep=""))))

```

```
)))$estimate[1]
```

```
,summary(pool(with(
```

```
data = mice.full.fit
```

```
, expr = eval(parse(text=paste('lm(l(', var., visit., ' - ', var., '.w0) ~ 0 + treat + sex + l(', var., '.w0 - mean(', var., '.w0)))', sep=''))))
```

```
)))$std.error[1]
```

```
,summary(pool(with(
```

```
data = mice.full.fit
```

```
, expr = eval(parse(text=paste('lm(l(', var., visit., ' - ', var., '.w0) ~ 0 + treat + sex + l(', var., '.w0 - mean(', var., '.w0)))', sep=''))))
```

```
)))$estimate[2]
```

```
,summary(pool(with(
```

```
data = mice.full.fit
```

```
, expr = eval(parse(text=paste('lm(l', var., visit., ' - ', var., '.w0) ~ 0 + treat + sex + l(', var., '.w0 - mean(', var., '.w0)))', sep=""))
```

```
)))$std.error[2]
```

```
,summary(pool(with(
```

```
data = mice.full.fit
```

```
, expr = eval(parse(text=paste('lm(l', var., visit., ' - ', var., '.w0) ~ 0 + treat + sex + l(', var., '.w0 - mean(', var., '.w0)))', sep=""))
```

```
)))$estimate[3]
```

```
,summary(pool(with(
```

```
data = mice.full.fit
```

```
, expr = eval(parse(text=paste('lm(l', var., visit., ' - ', var., '.w0) ~ 0 + treat + sex + l(', var., '.w0 - mean(', var., '.w0)))', sep=""))
```

```
)))$std.error[3]
```

```
,summary(pool(with(
```

```
data = mice.full.fit
```

```
, expr = eval(parse(text=paste('lm(l(', var., visit., ' - ', var., '.w0) ~ treat + sex + l(', var., '.w0 - mean(', var., '.w0)))', sep=''))
```

```
)))$estimate[1]
```

```
,summary(pool(with(
```

```
data = mice.full.fit
```

```
, expr = eval(parse(text=paste('lm(l(', var., visit., ' - ', var., '.w0) ~ treat + sex + l(', var., '.w0 - mean(', var., '.w0)))', sep=''))
```

```
)))$std.error[1]
```

```
,summary(pool(with(
```

```
data = mice.full.fit
```

```
, expr = eval(parse(text=paste('lm(l(', var., visit., ' - ', var., '.w0) ~ treat + sex + l(', var., '.w0 - mean(', var., '.w0)))', sep=''))
```

```
)))$estimate[2]
```

```

,summary(pool(with(

data = mice.full.fit

, expr = eval(parse(text=paste('lm(l(', var., visit., ' - ', var., '.w0) ~ treat + sex + l(', var., '.w0 - mean(', var., '.w0)))', sep=''))

)))$std.error[2]

))

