- current smokers of cigarettes/marijuana/e-cigarettes/vaporisers
- anyone unable to comprehend the study protocol or provide informed consent (i.e. due to English language or cognitive difficulties)
- do not own, or are not comfortable using, a smartphone and applications

Individuals with dietary restrictions or practices, including vegans and those with gluten or nut allergies will be excluded. Less restrictive dietary practices including vegetarians and those with lactose intolerance or specific dietary dislikes will be accommodated.

Pre-planned Sample size

An expected group difference is 0.46 mmol/L at 2-hrs after a glucose tolerance test (1). Our past data, DIRECT study (2) showed a mean glucose concentration of 7 mmol/L at two hours post meal. We note that $0.46/7.0$ is a 6.5% reduction. T4DM powered for a 0.6 mmol/L between group difference, which is approximately 6% change from baseline in a population including individuals with diabetes (3). We thereby assumed the MCID to be a 6% reduction from baseline in mean post meal AUC and use log (AUC) to estimate of the percentage difference between groups (4).

Using data from the DIRECT study (2), the SD of the log (meal test AUC) is expected to be 0.152 and pre-post AUC correlations were 0.87 at breakfast and 0.92 at dinner.

With $N=114$ (38 per group, randomized 1:1:1), a within-group SD of 0.152, pre-post correlation of at least 0.85 and a drop-out rate less than 10%, there is >80% to detect a difference of 0.06 in log-transformed AUC in a baseline adjusted ANCOVA ($\alpha = 0.027$ two-sided) (5).

Sample size adaption

None

Randomization details

Stratified random length blocked randomisation by sex (male or female) and fasting plasma glucose (≤ 6.0 vs >6.0 mmol/L)

STATISTICAL CONSIDERATIONS

Estimand Considerations

| | |
|--|---|
| Study objective 
 - To establish whether early or delayed time-restricted eating plus calorie restriction (eCR, dCR), improve markers of type 2 diabetes, compared with calorie restriction (CR) alone | |
| Estimand 
 - The difference in percentage change from baseline in the mean 2-hour post-meal glucose AUC levels after eight weeks of time restricted versus non-time restricted dieting, in obese men and women | |

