A secondary, complete-case sensitivity analysis will be performed for the analysis of the primary outcome and secondary efficacy outcomes in this analysis individuals with both baseline and week 8 assessments will only be included for each analysis.

As additional analysis will explore the treatment effects within subjects who were adherent to the protocol using data collected with the MyCircadianClock app plus the dietary checklists. This analysis will be reported in a secondary mechanistic publication of this study.

STATISTICAL METHODS

Primary Outcome

The primary analysis of the primary outcome is a covariate adjusted linear regression of the differences in PP glucose log AUC at 8 weeks from baseline. Covariates included will be treatment (three groups), baseline glucose log AUC, sex and fasting plasma blood glucose (as a continuous linear variable). Visual inspection of the residual distribution will be used to determine if assumptions of normality and the absence of a variance-mean association appear to be violated. If assumptions appear violated a generalized linear models will be considered with differing link functions will be considered and presented as sensitivity analyses. Given the limited sample size, no subgroup analyses are planned.

This analysis will be performed in all randomized individuals with individuals using multiple imputation using chained equations within treatment groups and combined using Rubin's rules. The variables used in the multiple imputation are age and sex; baseline and week 8 assessments of weight, PP glucose and insulin AUC (per meal), fasting glucose, fasting insulin and HbA1c; and the self-reported adherence over the 8 weeks and reason for discontinuation (related/unrelated to diet) if applicable. All concentrations will be imputed on the log scale, with the 3-meal mean of PP glucose and insulin AUC being calculated on the original scale after a back-transformation. Compliance will be imputed as per the intercurrent event strategies and the average compliance calculated over each period. Imputation will use multiple chained equations (*mice* R package), details of which are attached separately (file: *OMIT – Imputation code 2024-12-18.r*).

Secondary Efficacy Outcomes

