Appendix A: Results Tables.

Table A1: Primary outcome and confirmatory secondary outcomes with ordered testing procedure per comparison. Analyses from the prespecified multiply imputed analysis.

| | A: Est [95% CI] | B: Est [95% CI] | C: Est [95% CI] | AvC: Est [95% CI] | AvC p-value | BvC: Est [95% CI] | BvC p-value |
|------------------------|-----------------|-----------------|-----------------|-------------------|-------------|-------------------|-------------|
| PP glucose AUC | NA [NA; NA] | NA [NA; NA] | NA [NA; NA] | NA [NA; NA] | NA | NA [NA; NA] | NA |
| PP insulin AUC | NA [NA; NA] | NA [NA; NA] | NA [NA; NA] | NA [NA; NA] | * | NA [NA; NA] | * |
| Fasting insulin | NA [NA; NA] | NA [NA; NA] | NA [NA; NA] | NA [NA; NA] | * | NA [NA; NA] | * |
| Fasting glucose | NA [NA; NA] | NA [NA; NA] | NA [NA; NA] | NA [NA; NA] | * | NA [NA; NA] | * |
| HbA1c | NA [NA; NA] | NA [NA; NA] | NA [NA; NA] | NA [NA; NA] | * | NA [NA; NA] | * |

Table A2: Best-worst case sensitivity analysis of the primary analysis.

| | A: Est [95% CI] | B: Est [95% CI] | C: Est [95% CI] | AvC: Est [95% CI] | BvC: Est [95% CI] |
|------------------------|-----------------|-----------------|-----------------|-------------------|-------------------|
| PP glucose AUC | NA [NA; NA] | NA [NA; NA] | NA [NA; NA] | NA [NA; NA] | NA [NA; NA] |
| PP insulin AUC | NA [NA; NA] | NA [NA; NA] | NA [NA; NA] | NA [NA; NA] | NA [NA; NA] |
| Fasting insulin | NA [NA; NA] | NA [NA; NA] | NA [NA; NA] | NA [NA; NA] | NA [NA; NA] |
| Fasting glucose | NA [NA; NA] | NA [NA; NA] | NA [NA; NA] | NA [NA; NA] | NA [NA; NA] |
| HbA1c | NA [NA; NA] | NA [NA; NA] | NA [NA; NA] | NA [NA; NA] | NA [NA; NA] |

Table A3: Complete case sensitivity analysis of the primary analysis.

| | A: Est [95% CI] | B: Est [95% CI] | C: Est [95% CI] | AvC: Est [95% CI] | BvC: Est [95% CI] |
|------------------------|-----------------|-----------------|-----------------|-------------------|-------------------|
| PP glucose AUC | NA [NA; NA] | NA [NA; NA] | NA [NA; NA] | NA [NA; NA] | NA [NA; NA] |
| PP insulin AUC | NA [NA; NA] | NA [NA; NA] | NA [NA; NA] | NA [NA; NA] | NA [NA; NA] |
| Fasting insulin | NA [NA; NA] | NA [NA; NA] | NA [NA; NA] | NA [NA; NA] | NA [NA; NA] |
| Fasting glucose | NA [NA; NA] | NA [NA; NA] | NA [NA; NA] | NA [NA; NA] | NA [NA; NA] |
| HbA1c | NA [NA; NA] | NA [NA; NA] | NA [NA; NA] | NA [NA; NA] | NA [NA; NA] |

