## Assume control is group 'C'
```

```
imp.data$treat <- relevel(imp.data$treat, ref='C')
```

```

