## Construct log data to present analyses as percentage change.
```

```
for (var. in var.list[var.list %in% data.list$log.list]) {
```

```
for (visit. in c('w0', 'w8')) {  
  
  imp.data[,paste(var., visit., sep='.')] <- log(imp.data[,paste(var., visit., sep='.')])  
  
}; rm(visit.)  
  
}; rm(var.)
```

Variable lists

```
w0.list <- names(imp.data)[grepl('w0', names(imp.data))]
```

```
sum(!w0.list %in% names(imp.data)) # 0
```

```
w0.list <- w0.list[order(colSums(is.na(imp.data[,w0.list])))]; w0.list
```

```
w8.list <- names(imp.data)[grepl('w8', names(imp.data)) & !grepl('adher', names(imp.data))]
```

```
sum(!w8.list %in% names(imp.data)) # 0
```

```
w8.list <- w8.list[order(colSums(is.na(imp.data[,w8.list])))); w8.list
```

```
calculated.list <- c("adherence", "glucose.auc.w0", "insulin.auc.w0", "glucose.auc.w8", "insulin.auc.w8")
```

```
w0.list <- w0.list[!w0.list %in% calculated.list]
```

```
w8.list <- w8.list[!w8.list %in% calculated.list]
```

```
adher.list <- c('drop.out', 'week.drop', 'adher.w2', 'adher.w4', 'adher.w8')
```

```
sum(!adher.list %in% names(imp.data)) # 0
```

```
aux.list <- c("id", "treat", "sex");
```

```
sum(!aux.list %in% names(imp.data)) # 0
```

```
table(table(c(w0.list, w8.list, aux.list, adher.list, calculated.list))) # all 1s
```

```
sum(!names(imp.data) %in% c(w0.list, w8.list, aux.list, adher.list, calculated.list)) # 0
```

```

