## Include complete case analysis

if (MNAR.type == 1) {

output <- rbind(output, c(

c('CC')

, 'diff - orig'

, var.

```

```

, toupper(substring(visit.,2,3))

, summary(eval(parse(text=paste('lm(l(', var., visit., ' - ', var., '.w0) ~ 0 + treat + sex + l(', var., '.w0 - mean(', var., '.w0, na.rm=T)),
data=imp.data)', sep=''))))$coef[1,1:2]

, summary(eval(parse(text=paste('lm(l(', var., visit., ' - ', var., '.w0) ~ 0 + treat + sex + l(', var., '.w0 - mean(', var., '.w0, na.rm=T)),
data=imp.data)', sep=''))))$coef[2,1:2]

, summary(eval(parse(text=paste('lm(l(', var., visit., ' - ', var., '.w0) ~ 0 + treat + sex + l(', var., '.w0 - mean(', var., '.w0, na.rm=T)),
data=imp.data)', sep=''))))$coef[3,1:2]

, summary(eval(parse(text=paste('lm(l(', var., visit., ' - ', var., '.w0) ~ treat + sex + l(', var., '.w0 - mean(', var., '.w0, na.rm=T)),
data=imp.data)', sep=''))))$coef[2,1:2]

, summary(eval(parse(text=paste('lm(l(', var., visit., ' - ', var., '.w0) ~ treat + sex + l(', var., '.w0 - mean(', var., '.w0, na.rm=T)),
data=imp.data)', sep=''))))$coef[3,1:2]

))

}

```

```
}; rm(visit.)
```

```
}; rm(var., var.list)
```

```
rm(mice.full.fit)
```

```
}; rm(MNAR.type)
```

```
output
```

```
output <- as.data.frame(output)
```

```
names(output) <- c('analysis', 'type', 'var', 'visit', 'est.C', 'se.C', 'est.A', 'se.A', 'est.B', 'se.B', 'est.BvC', 'se.BvC', 'est.BvC', 'se.BvC')
```

```
for (col. in 5:ncol(output)) output[,col.] <- as.numeric(output[,col.]); rm(col.)
```

```

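### Under R's default coding, the per-arm changes for Tables A1–A4 are evaluated at the reference level of sex, not averaged over the men and women in the arm

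*SAP*

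**What the plan says.** The Analyses block of the imputation code regresses the week-8-minus-baseline change on treatment without an intercept, sex, and the baseline value minus its mean: "0 + treat + sex + l(', var., '.w0 - mean(', var., '.w0". The complete-case block has the same form: "0 + treat + sex + l(', var., '.w0 - mean(', var., '.w0, na.rm=T". In both, the first three coefficients and their standard errors are written out under the names "est.C', 'se.C', 'est.A', 'se.A', 'est.B', 'se.B". That order follows from making C the reference arm: "imp.data$treat <- relevel(imp.data$treat, ref='C".

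Sex is carried into the data as a plain variable. The code shown contains no centring of sex, sum contrast or marginal-mean step.

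The trial enrols both sexes and stratifies on sex (Randomization details): "Stratified random length blocked randomisation by sex (male or female". In Appendix A, Tables A1–A4 have the columns "A: Est [95% CI] | B: Est [95% CI] | C: Est [95% CI", with nothing to say that they refer to one sex. The text under Primary Outcome lists the covariates ("Covariates included will be treatment (three groups), baseline glucose log AUC, sex and fasting plasma blood glucose (as a continuous linear variable") but gives no rule for arm-level estimates, so the code is the only specification of them.

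**The concern.** Centring the baseline outcome is the step that lets a treatment coefficient in a no-intercept model be read as an arm mean. Done for baseline and omitted for sex, it leaves each coefficient tied to one level of sex.

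Readers will take the A, B and C columns as the average change on each diet, with its interval, and use them to judge whether glucose fell within each group. As coded, the columns answer a different question: the modelled change for a participant of the reference sex with average baseline. The same applies to the secondary outcomes, the meal-specific outcomes, weight, and both sensitivity analyses, because one loop produces them all.

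**Working it through.** **Inputs from the SAP (Pre-planned Sample size).** SD of log AUC 0.152; pre-post correlation at least 0.85; 38 per arm; dropout below 10%; difference 0.06; two-sided alpha 0.027.

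**Assumptions, because the SAP gives neither.** p, the share of participants of the non-reference sex, taken as equal across arms; g, the sex coefficient on the change.

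**The plan's own figure.** Residual SD s = 0.152 × √(1 − 0.85²) = 0.0801. With 38 × 0.9 ≈ 34 evaluable per arm, power for 0.06 at alpha 0.027 is 81.0%. The stated power above 80% reproduces, so s and n = 34 are the plan's own working values.

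**What the coefficients are.** Without an intercept, R gives treatment, the first factor, a full set of dummies and codes sex against its reference level. So:

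- coefficient for an arm = fitted change at mean baseline, reference sex
- adjusted arm mean = that coefficient + p × g

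A 0/1 numeric sex gives the same result. A 1/2 numeric sex would make the coefficient refer to neither sex.

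**Shift in the estimates.** Each arm is off by p × g. Fits with 38 per arm, p = 0.5 and g = −5 points (log scale × 100):

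| | C | A | B | A − C |
|---|---|---|---|---|
| Sex uncentred (as coded) | −4.0 | −10.0 | −7.0 | −6.0 |
| Sex centred | −6.5 | −12.5 | −9.5 | −6.0 |

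The shift is 0.5 × 5 = 2.5 points in every arm and cancels in the contrasts. Over p of about 0.3–0.7 and |g| of 2–5 points, the shift in the fits ran from about 0.6 to 3.6 points. These values only illustrate the formula.

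**Standard error.** The arm coefficient is the arm mean minus p times the estimated sex coefficient. The latter has variance s² / [3n·p(1 − p)] and, with arms balanced for sex, is uncorrelated with the arm means. Hence:

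- SE(as coded) = s × √{1/n + p² / [3n·p(1 − p)]}
- SE(arm mean) = s / √n = 0.0801 / √34 = 0.0137
- ratio = √{1 + p / [3(1 − p)]}, which does not involve g, s or n

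| p | SE as coded | Ratio to 0.0137 |
|---|---|---|
| 0.4 | 0.0152 | √1.222 = 1.11 |
| 0.5 | 0.0159 | √1.333 = 1.15 |
| 0.6 | 0.0168 | √1.500 = 1.22 |

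At p = 0.5 the 95% half-width is about 1.96 × 0.0159 = 0.031, against 1.96 × 0.0137 = 0.027 for an arm mean. This ignores chance imbalance in baseline and the between-imputation variance. The fits above, with their own baseline draws, gave ratios of 1.15–1.16 at p = 0.5 and 1.22–1.23 at p = 0.6.

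**The case against.** The strongest reply is that no planned inference depends on these columns. The estimand is a between-group difference, all analyses are framed as superiority of eCR and dCR over CR, and the only p-value columns belong to the comparisons with C. That stands: this is an error in descriptive columns.

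A second reply is that the inputs are partly hidden. The construction of the data set is not shown, so the coding of sex is inferred. The code also stops at a results object without filling a table, so the link to the A, B and C columns is inferred too. Both are fair qualifications. However, only sum contrasts or a pre-centred sex variable would lessen or remove the problem, and neither appears. The output names match the table columns, and no other source for those columns is given.

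A third reply is that a reference-level estimate is legitimate and its standard error is correct for that quantity. True, if it is labelled as such; Tables A1–A4 carry no such label.

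Four stronger readings are not supported:

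- **That the other sex is left out.** The model is additive and both sexes inform every coefficient.
- **That the treatment comparison is biased.** The offset is the same in all three arms and cancels. The imputed-data code does pick different coefficient positions for the contrasts than the complete-case code, but that is a separate matter.
- **That the shift should be judged against the 6% MCID.** That figure is used to power a between-group difference, which the shift does not touch.
- **That the arm estimates refer to a fasting glucose of zero.** The coded model has no separate, uncentred fasting glucose term.

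**Conclusion.** The point holds as a reporting error in the arm-level columns of Tables A1–A4. Under R's default coding, each column gives the model-adjusted change at the reference level of sex and mean baseline, not the adjusted arm mean.

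The estimates are displaced by p × g in all three arms. The SAP allows no figure for this, and it vanishes only if the sex coefficient is zero. The intervals are wrong for an arm mean whatever that coefficient is: about 11–22% too wide for p between 0.4 and 0.6, an assumed range with similar sex mix across arms. The primary test and the between-arm contrasts are not affected by this point. It is worth correcting because the columns are prespecified, sit beside the primary result, and cost almost nothing to put right.

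**What to change.** In the models that produce the arm-level estimates, replace sex by a 0/1 indicator minus its overall mean, as is already done for the baseline outcome. Alternatively, compute marginal means over the observed sex mix in each imputed data set and pool those. Make the same change in the complete-case code. If a further covariate is added to this model, such as the fasting plasma glucose that the text lists, centre it in the same edit. State under Tables A1–A4 that the A, B and C columns are adjusted means at average baseline and the observed sex mix.

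The cost is one or two lines of code and a table footnote. The treatment contrasts do not change, and no new data are needed.

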Hypothesis testing framework: All analyses are to test for superiority of eCR and dCR over CR.

Analyses: No interim analyses are planned. The analysis of the primary outcome will be conducted after the final subject has completed their 8 week assessment and the blood samples assessed for glucose concentrations.

Error Control: There are two primary comparisons, eCR vs CR and dCR vs CR with a common control and thereby use a Dunnett multi-test adjustment that controls the familywise error rate at 0.05 (two-sided) when each pairwise test uses an alpha of 0.027 (two-sided).

There are four secondary efficacy outcomes that will be tested to support a confirmatory finding: (i) PP insulin AUC, (ii) fasting insulin, (iii) fasting glucose, and (iv) HbA1c. An ordered testing procedure with per comparison (eCR vs CR and dCR vs CR) will be applied testing these four secondary outcomes in the order listed here, testing each subsequent outcome only if the previous outcome (and primary outcome) rejected the null. This procedure is applied separately for each comparison: eCR vs CR and dCR vs CR. The same pairwise alpha level, 0.027 (two sided), as the primary outcome will be applied to ensure that the familywise error rate is controlled at 0.05 (two-sided).

Standard multiplicity unadjusted 95% confidence intervals will be reported for all comparisons.

Covariate adjustment: All comparisons of treatment effect will include adjustment for...

1. The outcome variable's baseline assessment if appropriate,
2. Stratification factors (sex and baseline fasting plasma glucose as a continuous variable)

Sensitivity Analyses: A best-worst case sensitivity analysis will be performed for the analysis of the primary outcome and secondary efficacy outcomes.

- For all individuals missing the week 8 assessment in the CR (control) group the outcome will be imputed assuming missing-at-random. In other words, as if each individual's mean adherence was continued, or the cohort's mean adherence if no adherence data is available for an individual.
- For individuals missing the week 8 assessment in the eCR and dCR groups their outcome, a missing-not-at-random assumption will be applied by assuming zero adherence and outcomes imputed thereafter, i.e., assuming missing-at-random conditional on zero subsequent adherence.
- These assumptions will be made irrespective of the stated reason for diet discontinuation.

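### The multiple-imputation code outputs the control-arm intercept and A vs C as its two comparisons, and never outputs B vs C

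*SAP*

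**What the plan says.** SAP, Statistical Considerations, Error Control: "There are two primary comparisons, eCR vs CR and dCR vs CR with a common control". Table A1 in Appendix A reports these as AvC and BvC, each with an estimate, confidence interval and p-value, from the multiply imputed analysis.

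The appended R code implements this as follows.

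- **Reference arm.** The treatment factor is given C as its reference: "imp.data$treat <- relevel(imp.data$treat, ref='C". The level order is then C, A, B.
- **Arm means, MI block (Analyses section).** The model has no intercept, "w0) ~ 0 + treat + sex + l(', var., '.w0 - mean(', var., '.w0))))', sep", and elements 1, 2 and 3 are read.
- **Contrasts, MI block.** The model keeps the intercept, "w0) ~ treat + sex + l(', var., '.w0 - mean(', var., '.w0)))', sep". The code reads the estimate and standard error at position 1, then at position 2.
- **Contrasts, complete-case block.** The last two entries of that block fit the same intercept model and end in "data=imp.data)', sep=''))))$coef[2,1:2" and "data=imp.data)', sep=''))))$coef[3,1:2". They read rows 2 and 3. The same endings also occur earlier in the block on the no-intercept model, so the formula in front of them has to be read as well.
- **Column names.** "est.C', 'se.C', 'est.A', 'se.A', 'est.B', 'se.B', 'est.BvC', 'se.BvC', 'est.BvC', 'se.BvC". The BvC pair appears twice and there is no AvC.

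**The concern.** In an R linear model with an intercept, the first coefficient is the intercept, whichever arm is the reference. Positions 1 and 2 cannot be the two treatment contrasts, which sit at positions 2 and 3.

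The loop runs over both imputation scenarios (primary and best-worst) and 12 variables: the primary outcome, the four secondary efficacy outcomes, six meal-specific AUCs and weight. The most natural reading of the duplicated label is that the first BvC is a slip for AvC. On that reading, Table A1 would show the control arm's own change as A vs C, and A vs C as B vs C.

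All three arms are prescribed 30% calorie restriction, so a fall in glucose within the control arm is plausible even if meal timing has no effect. That fall would then appear as a treatment difference. Because the secondary outcomes are tested in order after the primary within each comparison, it could also open the gate for them.

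**Working it through.** **1. The plan's own power figure.** Inputs from the SAP's sample size section: 38 per group, SD 0.152, correlation 0.85, difference 0.06 in log AUC, two-sided alpha 0.027, dropout below 10%.

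- Residual SD = 0.152 × √(1 − 0.85²) = 0.080.
- At 38 × 0.9 = 34.2 per group, power is 81.3%. At 38 per group it is 85.4%.

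The stated power above 80% is reproduced. The concern does not depend on it, but the same inputs are used in step 5.

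**2. What each position holds, with levels C, A, B.**

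| Position | Model without intercept | Model with intercept | Read as a contrast by MI block | Read as a contrast by complete-case block |
|---|---|---|---|---|
| 1 | mean change, C | intercept (C at reference sex and mean baseline) | yes, first slot | no |
| 2 | mean change, A | A vs C | yes, second slot | yes, first slot |
| 3 | mean change, B | B vs C | no | yes, second slot |

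**3. Could the PDF conversion have lost a line?** An MI row has 4 identifiers + 6 arm-mean values + 4 contrast values = 14 entries, and the names vector has 14 entries, so nothing is missing. If the conversion had dropped a no-intercept term from the contrast formula, positions 1 and 2 would be the means of C and A, which are still not contrasts.

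**4. Numerical check.** Both formulas were fitted in R to one simulated data set without missing values: 38 per arm, C as reference, residual SD 0.08. Results on the percentage scale:

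| Quantity | Estimate (SE) |
|---|---|
| C mean, no-intercept model, position 1 | -4.727 (1.465) |
| Intercept, contrast model, position 1 | -4.727 (1.465) |
| A vs C, position 2 | -5.754 (1.874) |
| B vs C, position 3 | -4.710 (1.908) |

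The MI code would output -4.727 (1.465) and -5.754 (1.874). The correct pair is -5.754 (1.874) and -4.710 (1.908). The first contrast slot merely repeats the C mean already in the same row. The `mice` package was not available, so pooling was not run. Pooling averages each coefficient over imputations and does not change what a position means.

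**5. Size if the first slot were tested as a comparison.** Residual SD 0.080, 34 per arm (102 in all), an assumed 50:50 sex mix, no true difference between arms.

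- Intercept SE ≈ 0.080 × √(1/34 + 1/102) = 0.0159. The second term comes from evaluating the intercept at the reference sex rather than at the average.
- The SAP gives no expected change for the control arm, so a range is assumed. The table shows rejection at two-sided 0.027 in 4,000 simulated trials per scenario.

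| Assumed change in log AUC, control arm | First slot rejects |
|---|---|
| 0 | 2.8% |
| -0.02 | 16.8% |
| -0.03 | 36.7% |
| -0.04 | 60.5% |
| -0.06 | 92.3% |

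A normal approximation with SE 0.0159 gives about 37%, 61% and 94% for the last three rows, in close agreement.

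A separate simulation with 38 per arm, residual SD 0.08 and a change of -0.05 in every arm (2,000 runs) rejected in about 85% of runs for the intercept, against 2.4% to 2.8% for the true contrasts.

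**6. The second slot.** A true B effect of -0.06 has about 79% power at 34 per arm in simulation. In the MI rows its slot holds A vs C, which rejects about 2% to 3% of the time when A has no effect.

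**The case against.** The strongest reply is that the plan's governing text is right. The estimand table and the Statistical Methods section specify one regression with a three-level treatment factor, and Table A1 has separate AvC and BvC columns. On this view the fault lies in the extraction of results in an appended script, not in the choice of estimand or model. That is true, but the script is the dated, prespecified implementation of the primary analysis, and it does not deliver the comparisons the text requires.

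Four further points deserve weight.

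- **The code performs no test.** It stores estimates and standard errors only, so a later step, not shown, must produce p-values and intervals. The rejection rates in step 5 assume that this step uses the first slot unnoticed. They illustrate the consequence and are not a property of the plan.
- **The error may be noticed.** The first slot duplicates the control-arm mean in the same row, two columns share a name, and MI and complete-case rows would disagree. A careful analyst could well stop there. A prespecified code file should not rely on it.
- **B vs C is not lost everywhere.** The complete-case rows contain it. In the MI rows its point estimate can be recovered as the B mean minus the C mean. Its standard error cannot be recovered from the printed columns: in the example, combining the two arm-mean SEs as if independent gives 2.247 against the correct 1.908.
- **The control-arm change and the sex mix are assumed.** They affect the size of the distortion, not whether the wrong coefficients are read.

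**Conclusion.** The concern holds. As printed, the MI block reports the control-arm intercept and A vs C where A vs C and B vs C are required, and it omits B vs C from both the primary and the best-worst output for all 12 variables. This follows from the code alone and is confirmed by the complete-case block, which reads the right rows of the same model.

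The possible damage is large. For an assumed fall of 0.03 to 0.06 in log AUC in the control arm, and no difference between arms, the first slot would reject in about 37% to 92% of trials instead of 2.7% if it were tested as it stands. Those figures rest on the plan's SD and correlation, 34 per arm, an even sex mix and the assumed control-arm change. It must be fixed because it sits on the primary comparison.

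**What to change.** - In the MI contrast model, extract the estimates and standard errors by coefficient name (`treatA`, `treatB`), or use positions 2 and 3 as the complete-case block does. Names are safer because they survive a change of reference level or formula.
- Label the last four columns `est.AvC`, `se.AvC`, `est.BvC`, `se.BvC`. Relabelling alone is not enough, since the indices are wrong as well.
- Run the corrected code on a data set without missing values and confirm that the MI and complete-case rows agree.
- Re-issue the code file with a new date and a line in the SAP revision history, preferably before results are seen.

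The cost is a few lines of code and a re-issued file. No change to the design, data collection or sample size is needed.
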